### 3.4.2 Other Efficacy Endpoints

Additional efficacy endpoints include the following:

- Proportion of subjects alive and not mechanically ventilated over Day 1 through Day 28;
- Time to recovery (for hospitalized subjects at Screening), defined as the first day on which the subject has an NIAID score of 6 or larger;
- Time to recovery (for non-hospitalized subjects at Screening), defined as the second consecutive day on which the subject has an improvement in the NIAID ordinal scale by 1 point;
- Proportion of subjects alive and not in the intensive care unit over Day 1 through Day 28;
- Proportion of subjects alive and not in the hospital over Day 1 through Day 28;

- Proportion of subjects alive and not on supplemental oxygen over Day 1 through Day 28;
- Mortality; and
- Time to hospital discharge (for hospitalized subjects), defined as time from first hospital admission to first hospital discharge in the 28 day study period.

The proportions will be presented by treatment group (ADX-629 or placebo). The difference between treatment groups will be analyzed by a Generalized Estimating Equation (GEE) model similar to the MMRM model for the key efficacy endpoint if applicable. If the GEE model does not converge, then the Fisher's exact test will be used.

Time to recovery (censored at Day 28) from randomization and time to hospital discharge will be addressed by Kaplan-Meier analysis, including a comparison between the treatment groups by a log-rank test if applicable.

The mortality rate, calculated as the number of subjects who died by Day 28 divided by the number of subjects randomized, will be summarized by treatment group. The difference between treatment groups will be analyzed by Fisher's exact test if applicable.

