6.2 Screening Visit (Day -3 to 1)

The following procedures will be performed at Screening (Day -3 to 1):

- Obtain informed consent;
- Review inclusion and exclusion criteria;
- Obtain demographic information;
- Obtain medical/surgical history;
- Assess NIAID score (see Appendix C);
- Measure weight and height and calculate body mass index;
- Perform full physical examination;
- Measure vital signs;
- Perform PCR or another commercial or public health assay for SARS-CoV-2, and perform a confirmatory test for SARS-CoV-2 (if not done within 3 days [72 hours] of randomization), only if no documented, laboratory-confirmed SARS-CoV-2 infection test result is available;
- Perform serum hCG test (WCBP only);
- Perform FSH testing (naturally postmenopausal women only);
- Perform HIV, HBsAg, and HCV testing, only if status is unknown;
- Perform clinical laboratory assessments;
- Perform 12-lead electrocardiogram (ECG);

Note: ECG may be performed on Day 1, if not done at Screening, but it must be performed before the first dose of study drug is given.

- Perform chest X-ray;
- Record concomitant medications; and
- Record AEs.

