7.2 Secondary Endpoints

The key secondary endpoint is the NIAID ordinal scale score over Day 1 through Day 28.

Additional secondary endpoints include the following:

- Proportion of subjects alive and not mechanically ventilated over Day 1 through Day 28;
- Time to recovery (for hospitalized subjects at Screening), defined as the first day on which the subject satisfies 1 of the following 3 categories from the NIAID ordinal scale:
 - Hospitalized, not requiring supplemental oxygen – no longer requires ongoing medical care;
 - Not hospitalized, limitation on activities and/or requiring home oxygen; or
 - Not hospitalized, no limitations on activities;
- Time to recovery (for non-hospitalized subjects at Screening), defined as the second consecutive day on which the subject has an improvement in the NIAID ordinal scale by 1 point (e.g., NIAID scale 7 to 8);
- Proportion of subjects alive and not in the intensive care unit over Day 1 through Day 28;
- Proportion of subjects alive and not in the hospital over Day 1 through Day 28;
- Proportion of subjects alive and not on supplemental oxygen over Day 1 through Day 28;
- Mortality; and
- Time to hospital discharge (for hospitalized subjects).

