##### 3.1.3 *Definition of Baseline*

Baseline is defined as the last measurement prior to the first dose of study drug.

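### The recovery rule is chosen by hospital status at Screening, up to 3 days before the recovery clock starts, so a change of setting in between yields an uninformative or differently defined event

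*SAP*

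**What the plan says.** SAP 3.4.2 has two recovery endpoints, separated by setting at Screening. The inpatient one begins "Time to recovery (for hospitalized subjects at Screening", and its event is the first day with an NIAID score of at least 6. The other begins "Time to recovery (for non-hospitalized subjects at Screening", and its event is "the second consecutive day on which the subject has an improvement in the NIAID ordinal scale by 1 point". The score from which that improvement is counted is not given.

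Protocol 7.2 uses the same split; its inpatient definition reads "Time to recovery (for hospitalized subjects at Screening), defined as the first day on which the subject satisfies 1 of the following 3 categories", and the three categories are NIAID scores 6, 7 and 8.

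The analysis is of "Time to recovery (censored at Day 28) from randomization", by Kaplan-Meier with a log-rank comparison if applicable. Protocol 6.2 sets the Screening window: "The following procedures will be performed at Screening (Day -3 to 1". Randomization is a Day 1 procedure (Protocol 6.3.1), and dosing follows it on Day 1 (SAP 2.2.1).

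SAP 3.1.3 has a later anchor: "Baseline is defined as the last measurement prior to the first dose of study drug". It is not used to choose the recovery rule. Neither document says what happens to a subject whose setting changes between Screening and Day 1.

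**The concern.** The two rules describe different events. The inpatient rule asks whether the subject has reached a score of 6 or more, which every subject at home already has. The outpatient rule asks for a sustained gain over an earlier score, in practice from 7 to 8.

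When the setting changes between classification and time zero, the rule no longer fits the state from which follow-up starts. An inpatient discharged before Day 1 brings an automatic Day 1 event into the inpatient comparison. An outpatient admitted before Day 1 brings into the outpatient comparison an event that may occur while still in hospital, or may need a score of 8, depending on the reference score. With about 30 subjects split between two recovery analyses, one or two such records are visible in the curves.

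**Working it through.** The plan states no power, event rate or effect size for these endpoints, so there is no figure to reproduce. The check applies the rules as written to hypothetical score paths, then sizes the effect under stated assumptions.

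**Gap.** Screening runs from Day -3 to Day 1 (Protocol 6.2) and there is no Day 0 (SAP 3.1.1). The sequence is -3, -2, -1, 1, so classification precedes time zero by 0 to 3 days.

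**Can a switcher stay eligible?** Yes. Both settings are admitted (SAP 2.2.1), and only NIAID scores below 5 are excluded (Protocol 4.2), which leaves 5–6 (in hospital) and 7–8 (at home).

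**Case A: inpatient at Screening, home with score 7 on Day 1.** The Screening rule needs a score of at least 6, so the event is on Day 1. Under the rule matching the Day 1 setting, the event is the second consecutive day with a score of at least 7 + 1 = 8:

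| Score 8 starts on | Screening-status rule | Day 1-status rule |
|---|---|---|
| Day 5 | Day 1 | Day 6 |
| Day 10 | Day 1 | Day 11 |
| Day 20 | Day 1 | Day 21 |
| never | Day 1 | censored at Day 28 |

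**Case B: outpatient (7) at Screening, admitted before Day 1.** Scores are 5 on Days 1–5, 6 on Day 6, 7 on Days 7–14, and 8 from Day 15.
- Day 1-status (inpatient) rule: first score of at least 6, Day 6.
- Screening-status (outpatient) rule counted from the pre-dose score of 5: at least 6 on Days 6 and 7, so Day 7.
- Same rule counted from the Screening score of 7: at least 8 on Days 15 and 16, so Day 16; censored if 8 is never reached.

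Case B thus moves by 1 day, by 10 days or to censoring, according to a reference score that the SAP does not name.

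**How many subjects?** The documents give no rate. If a share m of 30 subjects changes setting, the expected number is 30m and the chance of at least one is 1 − (1 − m)^30:

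| Assumed m | Expected | Chance of at least one |
|---|---|---|
| 2% | 0.6 | 45% |
| 5% | 1.5 | 79% |
| 10% | 3 | 96% |
| 20% | 6 | >99% |

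With 2:1 allocation, one subject is 1/20 = 5% of the active arm or 1/10 = 10% of placebo.

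**What would reclassifying gain?** Assumed scenario: 10 vs 5 Screening inpatients, daily recovery chance 0.25 vs 0.10, and a fraction f in both arms already home on Day 1. With f = 0 the log-rank power is about 37%. Two separate simulations compared the Screening rule with an analysis from which the switchers are removed, as the fix would do:

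| f | First: Screening rule → switchers out | Gain (points) | Second: Screening rule → switchers out | Gain (points) |
|---|---|---|---|---|
| 10% | 32% → 33% | 1 | 30% → 33% | 3 |
| 20% | 26% → 28% | 2 | 24% → 29% | 5 |
| 30% | 22% → 26% | 4 | 20% → 25% | 5 |

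Gains are differences of rounded figures. Most of the fall from 37% remains after the fix, because there are then fewer inpatients to compare. What the moved subjects add to the outpatient analysis was not simulated.

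**The case against.** The strongest reply is that the plan does what it says. Protocol and SAP prespecify the same Screening anchor, and a subject hospitalized at Screening and now at home has reached one of the listed recovery categories. That stands in part: this is neither a conflict between the documents nor a misapplied rule. It does not make the Day 1 event informative, because the discharge came before treatment.

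A reader might infer bias between the arms. The documents do not support that: Screening status is fixed before randomization, so switchers fall to the arms by chance.

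A reader might also take the whole fall in power from 37% as the price of the Screening anchor. It is not; the fix returns only a small part of it, and every input to that scenario is assumed.

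Case B is narrow. Eligibility is reviewed again on Day 1 (Protocol 6.3.1), so an admitted subject must still score at least 5 and show no severe or critical signs. Its result also rests on the unnamed reference score, a second gap that meets the first one here.

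Finally, the stakes are low. These are additional secondary endpoints in an unpowered trial whose assessments the SAP calls exploratory (3.4), and NIAID and hospitalization data are listed anyway (3.4.1, 3.6.1). That stands, and it limits the weight of the point.

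**Conclusion.** The point holds as a minor defect of definition. Classification can precede time zero by up to 3 days, and nothing reclassifies a subject whose setting changes. A Screening inpatient who is home by Day 1 is recovered on Day 1 by construction, where the rule for the actual setting could give any later day or censoring. A Screening outpatient admitted before Day 1 is judged by a rule with no named reference score.

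The consequence is uninformative or differently defined events, not a tilt toward one arm. The frequency is unknown, and the effect is nil where the Screening and Day 1 settings agree, including whenever Screening is on Day 1. Under the assumed scenario (10 vs 5 inpatients, 0.25 vs 0.10 daily recovery, 10–30% switching), reclassifying gains about 1 to 5 points of inpatient log-rank power. The case for changing the rule is therefore clarity of what the event means more than power.

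**What to change.** In SAP 3.4.2, in both recovery definitions, replace status at Screening with status at baseline, meaning the last assessment before the first dose, in line with SAP 3.1.3. State that the outpatient 1-point improvement is counted from that same score. Record the departure from Protocol 7.2 in SAP Section 6, before unblinding.

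The cost is a wording change and a small documented difference between Protocol and SAP; no visit or measurement is added. One item must be confirmed first. Protocol 6.3.1 lists a Day 1 NIAID score without saying that it is taken before dosing, and outpatient scores come from a diary (Protocol 6.3). If the Day 1 score is not pre-dose, the last pre-dose value may be the Screening score, and the gap returns. No extra listing is needed, because the NIAID and hospitalization listings already show who changed setting.

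The change does not address subjects who start at the top of the scale or in hospital at 6; that is a separate question.

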#### 2.2.4 *Sample Size Determination*

Approximately 30 subjects will be randomized in a 2:1 ratio to 1 of 2 treatment groups: ADX-629 or placebo, both with standard of care treatment for COVID-19. This clinical trial is exploratory in nature and is not formally powered.

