## 3.4 Efficacy Assessment

Efficacy data (i.e., secondary endpoints) will be analyzed by randomized treatment based on the ITT Population. The key efficacy endpoint will also be analyzed based on the PP Population. The trial is exploratory and not formally powered. All assessments will be deemed exploratory.

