**Table 1. NIAID 8 Point Ordinal Scale for COVID 19**

Numerical Score	Definition
1	Death

2	Hospitalized, on invasive mechanical ventilation or extracorporeal membrane oxygenation
3	Hospitalized, on noninvasive ventilation or high-flow oxygen devices
4	Hospitalized, requiring supplemental oxygen
5	Hospitalized, not requiring supplemental oxygen – requiring ongoing medical care (COVID-19 related or otherwise)
6	Hospitalized, not requiring supplemental oxygen – no longer requires ongoing medical care
7	Not hospitalized, limitation on activities and/or requiring home oxygen
8	Not hospitalized, no limitation on activities

NIAID scores change from baseline to Day 28 will be summarized by treatment group (ADX-629 or placebo) using descriptive statistics (n, mean, standard deviation, median, minimum, and maximum).

All NIAID data will be listed.

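### Minor, and only if such subjects enrol: under SAP 3.4.2 a subject not hospitalized at Screening who starts and stays at NIAID 8 can never count as recovered, which caps the outpatient recovery curve and weakens its log-rank comparison

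*SAP*

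**What the plan says.** SAP 3.4.2 has two separate time-to-recovery endpoints, split by setting at Screening.

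- **Not hospitalized:** "the second consecutive day on which the subject has an improvement in the NIAID ordinal scale by 1 point". Protocol 7.2 has the same rule and gives a move from 7 to 8 as its example. Neither document names the score that improvement is measured from.
- **Hospitalized:** "defined as the first day on which the subject has an NIAID score of 6 or larger".

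On analysis, SAP 3.4.2 says "Time to recovery (censored at Day 28) from randomization and time to hospital discharge will be addressed by Kaplan-Meier analysis", with a log-rank comparison of the arms where applicable. SAP 3.4 says "Efficacy data (i.e., secondary endpoints) will be analyzed by randomized treatment based on the ITT Population", and SAP 3.2.1 defines that population as everyone randomized. No subset still able to recover is defined. SAP 3.1.3 does define a baseline: "Baseline is defined as the last measurement prior to the first dose of study drug".

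In SAP 3.4.1, Table 1, a score of 8 (at home, activities not limited) is the top of the scale, and 6 is still a hospitalized category. On size and status, SAP 2.2.4 says "Approximately 30 subjects will be randomized in a 2:1 ratio to 1 of 2 treatment groups" and SAP 3.4 says "All assessments will be deemed exploratory".

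**The concern.** A rise of one point from 8 does not exist. A subject who enters at 8 and never deteriorates has the best course the scale can record, yet the rule gives that subject no event. The subject stays in the risk set to Day 28 and is censored there, exactly like someone who was limited in activities throughout.

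If such subjects enrol, two things follow. The Kaplan-Meier curve for outpatients understates recovery, because it cannot rise above one minus the share who started at 8. The log-rank test also mixes subjects who can have the event with subjects who cannot, and a real difference becomes harder to see. The harm is to the interpretation of an exploratory endpoint, not to a confirmatory claim.

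**Working it through.** The plan gives no power, event rate or effect size for this endpoint, so there is no figure to reproduce.

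**1. Trace the rules day by day** (improvement taken from the starting score)

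- Not hospitalized, 8 on all 28 days: no event, censored at Day 28.
- Not hospitalized, 7 on Days 1 and 2, then 8: recovered on Day 4.
- Hospitalized, 5 on Days 1 to 3, then 6: recovered on Day 4.
- Hospitalized, 6 on Day 1: recovered on Day 1, in either arm.

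The unnamed reference score matters too. Read day against day, a move from 7 to 8 is one improvement and cannot occur on two days running, so the protocol's own example would fail. Read against baseline, it works.

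**2. Can a subject start at 8?** Protocol 4.2, item 1, excludes only scores below 5. Under Protocol 4.1, item 4, a symptom of mild illness can meet the symptom element, and oxygen saturation above 93% is among the example signs. Neither requires limited activity. However, inclusion item 5 and exclusion items 3, 4 and 7 to 9 are redacted.

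**3. Assumptions (none in the documents).** 14 versus 7 outpatients, in the planned 2:1 ratio. A share p of 0, 15, 30 or 50% starts and stays at 8. Time to improvement is exponential in whole days, and recovery is dated to the second day. Censoring is at Day 28, with a two-sided 5% log-rank test. The hazard ratio (HR) only sets the size of the effect; the SAP plans no Cox model.

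**4. Kaplan-Meier output, HR 2.5, placebo median 7 days.** Improvement must begin by Day 27 to be confirmed by Day 28, so

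Day-28 recovered share = (1 − p) × (1 − 2^(−27 × HR / median)).

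- Placebo, p = 0: 1 − 2^(−27/7) = 93.1%. With p = 30%: 0.70 × 93.1% = 65.2%.
- Drug, p = 0: 1 − 2^(−27 × 2.5/7) = 99.9%. With p = 30%: 0.70 × 99.9% = 69.9%.
- Difference: 6.8 points falls to 4.7.
- Median day (drug, placebo): 4 and 8 become 7 and 14. At p = 50% neither median is reached.

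**5. Log-rank power, simulated (6,000 trials per setting)**

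| Share at 8 | HR 2.5, 7 d: SAP rule | baseline below 8 only | HR 1.5, 21 d: SAP rule | baseline below 8 only |
|---|---|---|---|---|
| 0% | 42.2% | same | 9.8% | same |
| 15% | 14.5% | 35.9% | 7.6% | 9.0% |
| 30% | 7.3% | 29.3% | 5.9% | 8.9% |
| 50% | 4.8% | 21.7% | 4.0% | 7.9% |

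In the second case the gain is 9.0 − 7.6 = 1.4, 8.9 − 5.9 = 3.0 and 7.9 − 4.0 = 3.9 points.

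A separate simulation with other assumptions (all 30 subjects in one analysis, ratio 2, control hazard 0.06 per day, 20% at 8) gave 15% power with these subjects kept and 30% with them left out.

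**6. Null rejection (8,000 trials, median 7 days).** SAP rule: 6.4, 6.6, 5.6 and 5.3% at 0, 15, 30 and 50%. Restricted: 6.5, 7.2 and 7.7% at 15, 30 and 50%.

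**7. Inpatients starting at 6 (3,000 trials).** At 14 versus 7, HR 2.5 and 7 days, power is 44.1, 32.5, 22.7 and 16.2% at 0, 15, 30 and 50%; restricted, it is 37.2, 29.0 and 21.3%. At HR 1.5 and 21 days it is 9.2, 8.9, 8.6 and 8.5%; restricted, 9.8, 8.4 and 8.7%, so there is no consistent gain. At 6 versus 3 with 50% at 6, restricting lowers power from 9.9% to 5.9%.

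**The case against.** The strongest reply is that no such subject may exist. All elements of moderate severity must be met together, several criteria cannot be seen, the protocol's example suggests outpatients were expected to start at 7, and no baseline NIAID distribution is given. This stands: the shares above are assumptions, and at 0% there is no effect.

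It can also be said that the endpoint is exploratory, that the log-rank test is run only where applicable, that "All NIAID data will be listed", and that SAP 7 leaves detail to programming specifications, which are not available here. The first limits the severity. The others do not answer the point: the condition on the test does not say who is at risk, a listing does not alter the curve, and an endpoint definition belongs in the SAP.

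Three stronger readings are tempting and are not supported.

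- **That both recovery comparisons are materially weakened.** A reader might infer this because a hospitalized subject at 6 has the event on Day 1. That effect is smaller, restriction shows no consistent gain in the less favorable case, and it can lose power in a small group. A hospitalized 6 who meets the entry criteria also looks uncommon.
- **That every planned output understates the effect.** The gap between the Kaplan-Meier medians does not shrink; in step 4 it widens from 4 to 7 days.
- **That false positives rise under the SAP rule.** Step 6 shows no material inflation. It is the restricted test that is slightly more liberal, and part of its small gain at HR 1.5 reflects this: a rerun of the null at 21 days with 50% at 8 gave 6.1% restricted against 4.4%.

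**Conclusion.** The concern holds for the outpatient endpoint, as a minor and conditional point. That a subject who stays at 8 is never counted as recovered follows from the text alone. Whether it matters depends on how many such subjects enrol, which the documents do not show. The cap on the recovered share is exact for any number who start and stay at 8. The loss of power is large under a strong, fast effect and slight under a weak, slow one, and power is low in every case. Confidence is medium, because the group sizes, effect sizes and shares at 8 are all assumed. The inpatient rule merits a remark, not a change of analysis.

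**What to change.** Before unblinding:

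1. In SAP 3.4.2, define recovery for subjects not hospitalized at Screening as a score at least 1 point above the subject's own baseline (SAP 3.1.3) on two consecutive days, dated to the second day.
2. Run the outpatient time-to-recovery Kaplan-Meier and log-rank analyses in randomized subjects not hospitalized at Screening whose baseline score is below 8.
3. Tabulate baseline-8 subjects by arm, together with any later worsening, hospitalization or death, so that a subject who deteriorates does not drop out of sight.
4. State this as an exception to the ITT sentence in SAP 3.4 and list it in SAP 6, so that the sections agree.
5. For subjects hospitalized at Screening, report by arm how many score 6 on Day 1, and show that group descriptively if it is small.

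The cost is SAP wording only: no new data and no protocol amendment. The subset rests on a pre-dose score, so treatment cannot influence it. The downsides are fewer subjects (21 × 0.70, about 15, if 30% start at 8), a small-sample log-rank test that rejects about 7 to 8% of the time under the null with 30 to 50% at 8, and power that stays low.

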### 2.2 Study Design

#### 2.2.1 *Overview*

ADX-629-COVID-19-001 is a Phase 2a, randomized, double-blind, placebo-controlled, clinical trial to evaluate the safety, tolerability, efficacy, and PD of ADX-629, administered orally, in adult subjects with COVID-19 of moderate severity. Approximately 30 subjects will be randomized in a 2:1 ratio (ADX-629 to placebo) to receive either ADX-629 300 mg *bis in die* or twice daily (BID) or placebo BID for up to 28 days.

Treatment will begin on Day 1 following randomization. In addition to ADX-629 or placebo, all subjects will receive standard of care treatment for COVID-19. Treatment may commence whether a subject is hospitalized or is treated as an outpatient at Screening. During the Treatment Period (Days 1 to 28/End of Treatment [EOT]), all subjects will receive study drug (either ADX-629 or placebo) BID. The study drug will continue to be taken on an outpatient basis if a subject is discharged from the hospital prior to Day 28 for hospitalized subjects. If a subject is placed on mechanical ventilation and/or is otherwise unable to ingest an oral tablet, dosing will be stopped. However, the subject will continue to be monitored for efficacy and safety. Dosing of the study drug may resume once the subject is able to safely ingest an oral tablet.

All subjects will also have an assessment using the NIAID ordinal scale score daily on Days 1 to 28/EOT. The NIAID score will be evaluated directly for inpatient subjects and assessed via a subject diary for outpatient subjects through Day 28.

After treatment is completed, subjects will undergo a follow-up visit on Day 35 ( $\pm 3$  days) and a telephone follow-up on Day 60 ( $\pm 3$  days). The purpose of the telephone follow-up is to assess survival status and evaluate for COVID-19 relapse. A telephone follow-up visit may be performed in lieu of the Day 35 follow-up visit if the subject is unable to attend in person.

The schedule of study assessments is described in Appendix A.

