#### *3.6.1 Adverse Events (AEs)*

AEs will be captured from the date of informed consent through study completion. All AEs will be coded to system organ class and preferred term using MedDRA version 23.1.

Treatment-emergent adverse events (TEAEs) are defined as AEs that start after the first dose of study drug. AEs with partially missing onset dates will also be included as treatment emergent when the month (if it exists) and the year occur on or later than the month and year of the first dose date.

An overview of AEs will be provided including counts and percentages of subjects (and event counts) with the following:

- Any TEAEs (overall and by maximum severity)

- Any study drug related TEAEs
- Any serious AEs (SAEs)
- Any treatment-emergent serious AEs (TESEAEs)
- Any TEAEs leading to discontinuation of study drug
- Any AEs leading to death

Counts and percentages of subjects (and event counts) will also be presented by system organ class and preferred term for each of the categories in the overview.

Listings will be presented for all AEs and hospitalization data.

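### Time to hospital discharge is clocked from admission and not limited to subjects in hospital at entry, so outpatients admitted after randomization enter the log-rank comparison

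*SAP*

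**What the plan says.** The last of the additional endpoints in SAP 3.4.2 is time to hospital discharge for hospitalized subjects, "defined as time from first hospital admission to first hospital discharge in the 28 day study period". Protocol 7.2 has only "Time to hospital discharge (for hospitalized subjects", with no time origin, censoring rule or entry-status limit.

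The recovery endpoints in the same SAP list are treated differently. One is headed "Time to recovery (for hospitalized subjects at Screening" and its companion covers those not hospitalized at Screening. The analysis sentence reads "Time to recovery (censored at Day 28) from randomization and time to hospital discharge will be addressed by Kaplan-Meier analysis", so the Day 28 censoring and the randomization origin are attached to recovery only. A log-rank comparison follows, if applicable.

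The same list contains "Proportion of subjects alive and not in the hospital over Day 1 through Day 28". Protocol 3.1 and SAP 2.2.1 allow treatment to start in inpatients or outpatients, and SAP 3.4 analyzes efficacy by randomized arm in the ITT Population. SAP 6 (changes from the protocol) does not mention this endpoint.

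**The concern.** There are three separate problems.

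- **Population.** An entry outpatient contributes only if admitted after randomization. Treatment may change the chance and type of admission, so this part of the comparison is selected after randomization and is not protected by it.
- **Time origin.** The reference to the 28-day period can be read in two ways. If it limits only the discharge, entry inpatients bring in days before randomization, which treatment cannot affect. If it also limits the admission, subjects already in hospital drop out and the endpoint rests wholly on later admissions.
- **Death.** The SAP does not say how a death in hospital enters the Kaplan-Meier analysis.

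The selection problem matters most. A drug that prevents milder admissions leaves a sicker admitted group and can appear to lengthen stay. The endpoint of being alive and out of hospital would point the other way, and the plan has no rule for reading the two together.

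**Working it through.** The plan gives no figure for this endpoint, so there is none to reproduce. About 30 subjects at 2:1 is 20 on drug and 10 on placebo (SAP 2.2.4). All inputs below on inpatient share, admission and length of stay are assumptions.

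**1. Selection, all subjects entering as outpatients.** Suppose 4 of 10 placebo subjects are admitted, with stays of 4, 4, 14 and 14 days. Without prevention the drug arm of 20 would have four 4-day and four 14-day stays. Let the drug prevent some short stays and change nothing else. Placebo mean stay is 36/4 = 9.0 days, hospital days per randomized subject are 36/10 = 3.6, and 6/10 = 60% are never admitted.

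| Short stays prevented | Mean stay, drug (days) | Days per randomized subject, drug | Never admitted, drug | Log-rank chi-square | p |
|---|---|---|---|---|---|
| 25% | (3×4+56)/7 = 9.7 | 68/20 = 3.4 | 13/20 = 65% | 0.05 | 0.83 |
| 50% | (2×4+56)/6 = 10.7 | 64/20 = 3.2 | 14/20 = 70% | 0.25 | 0.62 |
| 75% | (4+56)/5 = 12.0 | 60/20 = 3.0 | 15/20 = 75% | 0.80 | 0.37 |
| 100% | 56/4 = 14.0 | 56/20 = 2.8 | 16/20 = 80% | 2.33 | 0.13 |

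The last row shows the log-rank calculation. At day 4, 8 are at risk (4 per arm), with 2 discharges, both on placebo. The drug arm has 0 observed against 1 expected, and the variance is 2 × ½ × ½ × 6/7 = 0.429, so chi-square = 1/0.429 = 2.33. At day 14 all who remain are discharged, which adds nothing.

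As prevention rises, mean stay moves against the drug while both per-randomized measures move in its favour.

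**2. Mixed population: make-up of the compared set.** Assume later admission risks of 10% on drug and 30% on placebo.

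| Inpatient share at entry | Entry inpatients, drug vs placebo | Expected later admissions | Later admissions as share of each arm's set |
|---|---|---|---|
| 20% | 4 vs 2 | 16×0.10 = 1.6 vs 8×0.30 = 2.4 | 1.6/5.6 = 29% vs 2.4/4.4 = 55% |
| 50% | 10 vs 5 | 1.0 vs 1.5 | 1.0/11 = 9% vs 1.5/6.5 = 23% |
| 80% | 16 vs 8 | 0.4 vs 0.6 | 0.4/16.4 = 2% vs 0.6/8.6 = 7% |

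**3. Mixed population: bias with no drug effect on stay.** This is a large-sample simulation with 90,000 subjects per scenario at 2:1. Assumed mean stays are 6 days for entry inpatients, 3 for mild later admissions and 10 for severe ones. Severe admission risk is 10% in both arms and mild admission risk is 20% on placebo. The results are discharge rate ratios, where a value below 1 makes the drug look worse.

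| Inpatient share | Equal mild risk | Drug halves mild admissions | Drug abolishes them |
|---|---|---|---|
| 20% | 1.00 | 0.89 | 0.73 |
| 50% | 1.01 | 0.96 | 0.88 |
| 80% | 0.99 | 0.98 | 0.97 |

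Restricting to entry inpatients and timing from randomization gives 0.99 to 1.02 in every scenario.

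**4. Time origin, all subjects entering as inpatients (20 vs 10).** The simulation has 3,000 runs, exponential time to discharge, placebo median 7 days, hazard ratio 2, censoring at Day 28 and uniform prior stay.

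| Days in hospital before randomization | Power from randomization | Power from admission |
|---|---|---|
| 0–3 | 40.3% | 39.8% |
| 0–7 | 38.5% | 36.0% |
| 0–14 | 38.4% | 29.2% |

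Repeat runs put the last figure at 29 to 31%. Type I error is 5.9 to 6.5% throughout, so the admission origin costs power without creating bias.

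**5. Death.** Assume 10 inpatients, with 2 deaths on Day 5 and 8 discharges on Days 6 to 13. If deaths are censored, the Kaplan-Meier estimate of discharge by Day 28 is 100%. If they are kept as not discharged it is 8/10 = 80%.

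**The case against.** The strongest reply is that the restriction to hospitalized subjects may be meant to cover those in hospital when treatment starts. The design overview in both documents can be read that way where it describes discharge before Day 28. On that reading the selection problem disappears. It is possible, but no passage states it. In the Day 1, 7, 13, 22 and 28 visit lists (Protocol 6.3) the same term means current status. An origin at first admission within the study period fits later admissions more naturally, and the neighbouring bullets spell out status at Screening. Even if it were the intent, the admission origin would remain.

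Other points stand in part:

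- The origin alone does little harm. Visible power loss needs long prior stays, which entry with moderate disease and Screening from Day -3 make less typical.
- The examples in steps 1 and 4 are opposite extremes, all outpatients and all inpatients. A mixed population weakens both.
- None of the wrong-direction results in step 1 is significant.
- SAP 3.4 says "All assessments will be deemed exploratory", the test is run only if applicable, and SAP 3.6.1 says "Listings will be presented for all AEs and hospitalization data". A reader could therefore separate entry from later admissions afterwards.
- The SAP is equally silent on deaths in time to recovery.

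These points limit the consequence. They do not make the definition sound.

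**Conclusion.** The concern holds. The admission origin is explicit in the SAP. Nothing limits the analysis to subjects hospitalized at entry, so as written it admits a group selected after randomization. The likely direction of error is against a drug that prevents mild admissions.

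The size depends on quantities the documents do not give. Under the mixed-population assumptions, the discharge rate ratio ranges from 0.73 (20% inpatients, mild admissions abolished) to 0.98 (80% inpatients, mild admissions halved) when the true effect on stay is nil. The bias vanishes if few outpatients are admitted or if admission risks are equal. No decision rule rests on this endpoint. It should be corrected because it can mislead and the correction is cheap; it does not threaten the trial's primary objective.

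**What to change.** Redefine the endpoint as time from randomization to first discharge alive, in subjects hospitalized at randomization, censored at Day 28. Keep in-hospital deaths in the analysis as not discharged through Day 28. Take discharge as the first day with an NIAID score of 7 or 8. Leave later admissions of entry outpatients to the ITT endpoint "Proportion of subjects alive and not in the hospital over Day 1 through Day 28" and list them descriptively. Report the number of entry inpatients per arm beside the curve.

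The cost is SAP wording before database lock. No new data are needed: SAP 2.2.1 states "All subjects will also have an assessment using the NIAID ordinal scale score daily on Days 1 to 28/EOT", and the scale separates in hospital (2–6), out of hospital (7–8) and death (1). The downside is a smaller analysis set, about 4 vs 2 subjects at a 20% inpatient share. In that case show the data descriptively, which the SAP's provision for testing only where applicable already allows.
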